## 8 STUDY POPULATION

Subjects with CF <24 months of age at treatment initiation who have an ivacaftor-responsive *CFTR* mutation on at least 1 allele.

- Subjects will be eligible in countries/regions where ivacaftor is approved for use in subjects 2 years of age and older. A list of approved ivacaftor-responsive *CFTR* mutations is included in the study manual. If ivacaftor is approved for additional mutations in any country/region, a memorandum will be sent to investigative sites in that country/region and subjects with the newly approved mutations will also be eligible.
- Investigators should consult the approved ivacaftor label in their country/region to confirm approved mutations for subject eligibility.

The study is open to subjects who meet all inclusion and exclusion criteria. Subjects will be drawn from 2 sources:

- Subjects who completed Study 124 Part B and elect to enroll in Study VX15-770-126 (Study 126)
- Subjects who did not participate in Study 124 Part B, which includes
  - subjects who participated in Study 124 Part A only
  - subjects who did not participate in Study 124 Part A or B

Eligibility will be reviewed and documented by an appropriately qualified member of the investigator's team before subjects are enrolled.

### 8.1 Ivacaftor Arm: Subjects From Study 124 Part B

#### 8.1.1 Inclusion Criteria

1. Subjects transitioning from Study 124 Part B must have completed the last study visit of Study 124 Part B

Added guidance:

- Subjects who had a study drug interruption at the last scheduled visit of Study 124 Part B, subjects who required study drug interruption that was to be continued or initiated at Day 1 in Study 126, or subjects who resumed study drug in Study 124 Part B after a study drug interruption due to elevated transaminases but who did not complete at least 4 weeks of rechallenge with study drug (due to the timing of the rechallenge versus the time remaining in Study 124 Part B) must meet eligibility criteria and have received approval from the Vertex medical monitor.
2. For Gap Transition subjects: hematology and serum chemistry results at baseline with no clinically significant abnormalities that would confound the study assessments or pose an additional risk to administering ivacaftor to the study subject, as judged by the investigator.
  3. As judged by the investigator, parent or legal guardian must be able to understand protocol requirements, restrictions, and instructions; and must sign the informed consent form (ICF).

### 8.1.2 Exclusion Criteria

1. History of any illness or condition that, in the opinion of the investigator, might confound the results of the study or pose an additional risk in administering ivacaftor to the subject. Examples of subjects who may not be eligible include
  - subjects with a history of allergy or hypersensitivity to the study drug; and
  - subjects with severe or life-threatening reactions to the study drug in Study 124.
2. Subjects receiving commercially available ivacaftor treatment

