**Table 3-2 Schedule of Assessments for VX15-770-126 (Ivacaftor Arm: Gap Transition Subjects From Study 124 Part B)**

Event/Assessment	Day -28 to Day -1	Treatment Period (Day 1 through Week 96)			ETT Visit a	Safety Follow-up Visit b	24-Week Follow-up OE
		Day 1 c	Weeks 12, 36, 60, and 84 (±7 Days)	Weeks 24, 48, 72, and 96 (±7 Days)	As Soon as Possible After the Last Dose	4 Weeks (±7 Days) After the Last Dose	24 Weeks (+ 14 Days) After the Last Dose
Ophthalmologic examination l		X m		X	X n		X
Fecal sample collection o		X		X	X		
Sweat chloride test p		X		X			
Qualitative microbiology cultures		X		X			
Multiple breath washout (optional) q		X		X r			

k If the Day 1 Visit is conducted ≤9 days after the last study visit of Study 124 Part B, the serum chemistry and hematology assessments performed at the last study visit of Study 124 Part B will not need to be repeated. If the Day 1 Visit is conducted >9 days after the last study visit of Study 124 Part B, the serum chemistry and hematology assessments can be obtained up to 9 days before or at the Day 1 Visit. The results must be reviewed before the first dose of study drug.

l The OE will be conducted by a licensed ophthalmologist, preferably a pediatric ophthalmologist. The OE may be performed at the study visit or ± 14 days of the clinic visit.

m The OE does not need to be repeated if the subject had an OE in Study 124 Part B within 24 weeks of the Day 1 Visit. Otherwise, an OE must be conducted within 14 days of the Day 1 Visit. Throughout this study, these subjects should have OEs approximately every 24 weeks (± 14 days) from the last OE in Study 124.

n The OE for the ETT Visit will be conducted for all subjects who prematurely discontinue ivacaftor dosing (for any reason) unless performed in the last 12 weeks.

o Samples will be analyzed for fecal elastase-1 and other markers of intestinal inflammation, including fecal calprotectin. Samples may be collected (e.g., at home) up to 24 hours before the study visit (e.g., at home) and brought to the clinic. If the sample is collected in the clinic, the sample may be collected pre- or postdose.

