## 8.2.2 Exclusion Criteria

1. History of any illness or condition that, in the opinion of the investigator, might confound the results of the study or pose an additional risk in administering ivacaftor to the subject
2. An acute upper or lower respiratory infection, or pulmonary exacerbation, or changes in therapy (including antibiotics) for pulmonary disease within 4 weeks of Day 1
3. Known colonization with organisms associated with a more rapid decline in pulmonary status (e.g., *Burkholderia cenocepacia*, *Burkholderia dolosa*, and *Mycobacterium abscessus*). A subject is excluded if they have a positive culture of one of these organisms.
4. Abnormal liver function at screening or any prior history of clinically relevant elevated ( $>2 \times$  upper limit of normal [ULN]) serum aspartate transaminase (AST), serum alanine transaminase (ALT), or bilirubin (excluding newborn hyperbilirubinemia, e.g., physiologic jaundice or breastmilk jaundice of the newborn)
5. Hemoglobin  $<9.5$  g/dL at screening
6. History of solid organ or hematological transplantation
7. Any clinically significant “non-CF-related” illness within 2 weeks of Day 1. “Illness” is defined as an acute (serious or nonserious) condition (e.g., gastroenteritis)
8. Use of any moderate or strong inducers or inhibitors of cCYP3A within 2 weeks of Day 1
9. Participation in a clinical study involving administration of either an investigational or a marketed drug within 30 days or 5 terminal half-lives (whichever is longer or as determined by the local requirements) before screening. Note: Participation in a noninterventional study (including observational studies, registry studies, and studies requiring blood collections without administration of study drug) is permitted.
10. Chronic kidney disease of Stage 3 or above
11. Unable to undergo an adequate slit-lamp examination at screening
12. Presence of a lens opacity or cataract identified at the screening OE (excluding those considered congenital and nonprogressive, such as a suture cataract)

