#### **9.7 Removal of Subjects**

Subjects may withdraw from the study at any time at their own request. Subjects may be withdrawn from study drug treatment at any time at the discretion of the investigator or Vertex for safety, behavior, noncompliance with study procedures, or administrative reasons. If a subject has been withdrawn from study drug treatment, the subject should continue to be followed through the ETT, Safety Follow-up, and OE Follow-up Visits, as indicated in Sections 9.1.1.3 and 9.1.1.5, provided the subject's parent or legal guardian has not withdrawn consent.

If a subject does not return for a scheduled visit, reasonable effort will be made to contact the subject's parent or legal guardian. In any circumstance, reasonable effort will be made to document subject outcome. The investigator will inquire about the reason for withdrawal, request that the subject's parent or legal guardian return all unused investigational product(s), request that the subject return for a Safety Follow-up Visit, if applicable (see Section 9.1.1.5), and follow up with the subject's parent or legal guardian regarding any unresolved adverse events (AEs).

If the subject's parent or legal guardian withdraws consent for the study, no further evaluations will be performed and no additional data will be collected. Vertex may retain and continue to use any data collected before such withdrawal of consent.

A subject **will be** discontinued from study treatment for any of the following reasons:

- Vertex, regulatory authorities, or the site's IRB or ethics committee (EC) closes the study.
- A subject is noncompliant with study protocol requirements, restrictions, and instructions to an extent that is considered unacceptable by the investigator or Vertex medical monitor.
- A subject participates in another interventional clinical study.
- A subject develops a new lens opacity or cataract (see Section 11.6.5).

A subject **may be** discontinued from study treatment, after discussion between the investigator and the Vertex medical monitor, for any of the following reasons:

- A subject develops a medical condition that requires prolonged concomitant therapy with a prohibited medication or prolonged interruption of ivacaftor.
- A subject develops a life-threatening adverse event or a serious adverse event (SAE) that places them at immediate risk.
- A subject has an increase in liver function test levels (LFTs; e.g., AST or ALT levels) as described in Section 11.6.2.

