- Clinically significant findings are observed in the slit-lamp examination.

During the course of the study, if ivacaftor is approved and available for the treatment of CF in populations enrolled in this study, subjects may be discontinued at the discretion of the sponsor. If a subject is switching to commercially available ivacaftor, the ETT Visit (Section 9.1.1.5) will be completed before dosing with commercial drug begins, and the Safety Follow-up Visit will not be required.

Alternatively, if local health authorities decline to approve ivacaftor, or if ivacaftor cannot be given to patients within a given age cohort (e.g., an appropriate dose cannot be determined), then subjects of the relevant populations may be discontinued after communication to investigators and IRBs/IECs of the benefits/risks for the relevant subject population. If subjects are discontinued from the study, an ETT Visit should occur as soon as possible after the last dose of study drug and a Safety Follow-up Visit should occur within 4 weeks ( $\pm$  7 days) after the last dose of study drug.

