#### **11.6.5 Ophthalmologic Examinations**

All subjects should have an OE approximately every 24 weeks while on ivacaftor treatment in this study. Subjects who did not participate in Study 124 Part B should have an additional OE exam at Week 12. The OE must be conducted by a licensed ophthalmologist, preferably a pediatric ophthalmologist. Whenever possible, the same ophthalmologist should perform the OEs throughout the study. The OE will include the following:

- Examination of the lens with a slit-lamp (portable or otherwise; pharmacologically dilated examination)
- Assessment of the red reflex (pharmacologically dilated examination)

- Screening OEs (subjects not from Study 124 Part B only): examination of the fundus (retina, optic nerve, and vessels), pupils, and eye movements

For subjects not from Study 124, relevant medical history (e.g., history of steroid use; history of trauma to the eye; and family history of glaucoma, congenital cataracts, or cataracts arising later in life) will be collected at screening. For subjects from Study 124 Part B with a Same-day Transition, the above relevant ophthalmological medical history will be collected in Study 124. For subjects from Study 124 Part B with a Gap Transition, the above relevant ophthalmological history will be collected before or at the Day 1 Visit.

During the screening period, if an adequate slit-lamp examination cannot be conducted, subjects will not be enrolled until an adequate repeat slit-lamp examination is completed (Sections 9.1.1.1.1 and 9.1.1.1.3) and eligibility criteria regarding the ophthalmologic findings are met.

If a new lens opacity or cataract is identified at any OE in subjects in the ivacaftor arm, study drug dosing must be discontinued. The-Vertex medical monitor should also be notified.

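### Part B rollovers have no lens-opacity exclusion, so a Gap child whose Day 1 eye examination is waived could restart ivacaftor with an opacity first seen in Part B

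*Protocol*

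**What the plan says.** Rollover entry is governed by protocol 8.1. The first inclusion criterion concerns completion: "Subjects transitioning from Study 124 Part B must have completed the last study visit of Study 124 Part B". The second concerns blood results, for Gap children only, and the third concerns consent. There are two exclusions: an investigator-opinion clause, whose examples are hypersensitivity and "subjects with severe or life-threatening reactions to the study drug in Study 124", and current commercial ivacaftor. None of the five mentions the lens, the slit lamp or an OE.

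Children not from Part B have a similar investigator-opinion clause (8.2.2 #1). They must also be able to undergo an adequate slit-lamp examination (#11), and #12 excludes them for: "Presence of a lens opacity or cataract identified at the screening OE (excluding those considered congenital and nonprogressive, such as a suture cataract".

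On the Day 1 OE of a Gap child, Table 3-2 footnote m says: "The OE does not need to be repeated if the subject had an OE in Study 124 Part B within 24 weeks" of Day 1. It adds: "Throughout this study, these subjects should have OEs approximately every 24 weeks (± 14 days) from the last OE in Study 124". Section 9.1.1.2.1 repeats both rules.

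On treatment, 11.6.5 says: "If a new lens opacity or cataract is identified at any OE in subjects in the ivacaftor arm, study drug dosing must be discontinued". Section 9.7 lists among its mandatory reasons for stopping: "A subject develops a new lens opacity or cataract". Among its discretionary reasons, after discussion with the medical monitor, it lists: "Clinically significant findings are observed in the slit-lamp examination". Neither section says what an opacity must be new relative to.

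**The concern.** Section 9.2.3 explains that the OEs are there because newborn rats given ivacaftor developed lens opacities. An opacity that appears after a child has begun ivacaftor is therefore the finding the protocol most wants to act on, and rollovers are the children already exposed. The entry rules nevertheless screen the lens only in children not from Part B.

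At stake is consistency between entry and stopping. The same finding that must end dosing when first seen at a Study 126 OE need not prevent dosing from restarting when it was first seen at the last Part B OE. On one reading of *new*, it need not end dosing afterwards either.

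**Working it through.** No figure in the plan bears on this point, so the check is to trace each entry route through the rules.

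| | Not from Part B | Same-day rollover | Gap, Day 1 OE done | Gap, Day 1 OE waived |
|---|---|---|---|---|
| Investigator-opinion exclusion | 8.2.2 #1 | 8.1.2 #1 | 8.1.2 #1 | 8.1.2 #1 |
| Lens exclusion | 8.2.2 #12 | none | none | none |
| OE belonging to entry | screening OE | Part B Week 24 OE reused, or an OE within 14 days of the visit (Table 3-1 footnotes c, i) | OE within 14 days of Day 1 (footnote m) | none in Study 126 |
| First OE at which the stop can act | entry already barred | Day 1 OE | Day 1 OE | next scheduled OE, and only if the opacity still counts as new |

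1. **Same-day.** Footnote c of Table 3-1 takes the Day 1 results from the Part B Week 24 Visit. The final Part B OE, when used, therefore serves as the Study 126 Day 1 OE. If the OE is done after Day 1, it is plainly a Study 126 examination. Either way, the stop in 11.6.5, which covers any OE in the ivacaftor arm, most naturally applies.

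2. **Gap, OE waived.** The opacity was seen in Study 124 and there is no Day 1 OE. If *new* means since ivacaftor began, the stop applies. If it means new in Study 126, it does not, and only the discretionary slit-lamp provision in 9.7 remains.

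3. **Do the baseline definitions settle it?** They point in different directions. SAP Appendix B, Table 11-4, takes the rollover OE baseline from the parent study, which fits the first reading. Protocol 12.3.1 measures a Gap child's changes from the Study 126 baseline. With the Day 1 OE waived, that baseline is the last Part B OE, where the opacity was already present. Both are analysis definitions and neither governs stopping.

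4. **Is the earlier result reviewed before dosing?** For a Gap child's chemistry and hematology, yes: 8.1.1 #2 makes them an entry criterion, and footnote k and 9.1.1.2.1 require review before the first dose. No such sentence exists for the OE. The slit-lamp hold in 11.6.5 is tied to the screening period, which the synopsis limits to children not from Part B. Even if the pre-Day 1 column of Table 3-2 brought Gap children within it, the hold enforces ophthalmologic eligibility criteria, and 8.1 has none.

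5. **Time to the next OE.** Under footnote m, 24 × 7 = 168 days, so the next OE falls between 168 − 14 = 154 and 168 + 14 = 182 days after the last Study 124 OE. Let g be the days from that OE to Day 1; the waiver requires g ≤ 168. The next OE then falls 154 − g to 182 − g days after Day 1. The documents do not give g. At g = 1 the range is 153 to 181 days. At g = 168 it is 14 days either side of Day 1.

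**The case against.** The case on the other side is substantial.

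- **Discretionary controls.** The line quoted from 8.1.2 is one of several non-exhaustive examples, and the clause itself lets an investigator exclude any condition that adds risk. Eligibility must be reviewed and documented before enrollment (section 8). A child whose drug was interrupted at the last Part B visit needs medical-monitor approval (8.1.1 #1). This stands, but all of it is judgment. For children not from Part B, the protocol did not rely on the same kind of clause for lens findings.
- **A narrow path.** Children who stopped ivacaftor early in Part B are directed to the observational arm (8.3.1). What remains is essentially an opacity first seen at the last Part B OE. Study 124 may also have its own cataract rule, or may require that OE to be read before rollover. This stands and cannot be checked.
- **A legitimate design difference.** A Same-day child's Day 1 is in effect another on-treatment visit with a parent-study baseline, so a clean-entry examination is less needed. This stands for Same-day children. It does not answer the Gap child who is being started again.

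A reader might infer that every rollover is affected, because no OE result is required before the first Study 126 dose and the Day 1 OE may fall 14 days late (14 × 2 = 28 doses at q12h). The documents do not support that as a defect of entry. The same 14-day allowance applies to the OEs at Weeks 24, 48, 72 and 96, and the stop acts once a late Day 1 OE is read.

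**Conclusion.** The point holds for one group: Gap Transition children whose Day 1 OE is waived. Such a child with an opacity first seen in Part B can be restarted subject only to investigator judgment, and the mandatory stop may not apply because *new* is undefined. For Same-day children, and for Gap children who have a Day 1 OE, the stop most naturally applies already.

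The size is small. The number of affected children is not given and may be zero, and repeat OEs about every 24 weeks limit how long an opacity goes unexamined. Nothing in the documents shows that a child with an opacity was enrolled, and that should not be inferred. The conclusion assumes that Study 124 did not itself block such a child, which these documents cannot confirm. This is a minor safety alignment between the entry rule and the protocol's own stopping rule.

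**What to change.** (a) Add an exclusion to 8.1.2 for a lens opacity or cataract at the most recent available Study 124 OE, or at the Day 1 OE if that is done before dosing. Keep the exception in 8.2.2 #12 for congenital, nonprogressive findings. Require that existing result to be reviewed when eligibility is confirmed. No extra examination is needed.

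(b) In 9.7 and 11.6.5, define *new* as absent at the Study 124 baseline OE for rollovers and at the screening OE for others. This also makes explicit that an opacity found at a Same-day child's OE done after Day 1 triggers the stop.

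(c) Amend 8.3.1 so that a completer excluded under (a) can be followed in the observational arm. At present it admits only completers who chose not to enroll in the ivacaftor arm and children who stopped early.

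Do not narrow the Day 1 OE window for Same-day children. Requiring the OE before dosing could delay Day 1, turn the child into a Gap subject and interrupt therapy.

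The cost is one criterion with a review sentence, one definition and one clause, with the possible loss of very few rollover children from the ivacaftor arm. The SAP is for the final analysis, so enrollment may already be closed. In that case the entry edits come too late, but the definition in (b) can still be used for reporting, with a listing of each rollover's last Study 124 OE and Day 1 OE results.

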### 8.2 Ivacaftor Arm: Subjects Not From Study 124 Part B

Subjects not from Study 124 Part B will only be allowed to enroll in Study 126 after an adequate number of subjects have completed the corresponding age cohort in Study 124, in conjunction with feedback from regulatory authorities.

#### 8.2.1 Inclusion Criteria

1. Age <24 months at the Day 1 Visit
2. Confirmed diagnosis of CF, defined as a sweat chloride value  $\geq 60$  mmol/L by quantitative pilocarpine iontophoresis or 2 CF-causing mutations
  - If the results of the sweat chloride and/or the genotype test are documented in the subject's medical record, and the historic genotype result is approved by the Vertex medical monitor, the tests do not need to be performed at screening. A sweat chloride test must be performed if the sweat chloride value is not available in the subject's medical records and the value is needed to establish eligibility.
3. An ivacaftor-responsive *CFTR* mutation on at least 1 allele. Subjects will be eligible in countries/regions where ivacaftor is approved for use in subjects 2 years of age and older.
  - If a genotype test has been performed previously and is documented in the subject's medical record, the subject's eligibility must be approved by the Vertex medical monitor. If a historic genotype result is not available at screening or if the historic genotype result is not approved by the Vertex medical monitor, the subject will undergo *CFTR* genotype screening and the results must be reviewed before the first dose of ivacaftor. Subjects who have been enrolled and whose screening genotype does not confirm study eligibility will not receive study drug.
4. Hematology, serum chemistry, and vital signs results have no clinically significant abnormalities that would confound the study assessments, as judged by the investigator.
5. Weight at screening must be within the weight limits as defined for the study drug dose levels (Section 9.2.2) or according to the dosing guidelines identified in the "Justification for Dose Selection" memorandum effective at the time a subject is screened.
6. For subjects <3 months of age only, gestational age  $\geq 38$  weeks.
7. As judged by the investigator, parent or legal guardian must be able to understand protocol requirements, restrictions, and instructions; and must sign the ICF.

